4.1. General Considerations

This information will be copied directly from the protocol. Additional general considerations may be added. Statistical analysis of this study will be the responsibility of Eli Lilly and Company (Lilly) or its designee. All statistical analyses will be conducted with SAS Version 9.4 or higher and R Version 4.1.2 or higher unless otherwise stated. Any change to the data analysis methods described in the protocol will require an amendment ONLY if it changes a principal feature of the protocol. Any other changes to the data analysis methods described in the protocol, and the justification for making the change, will be described in the SAP or the clinical study report (CSR). Some analyses and summaries described in this analysis plan may not be conducted if not warranted by data (eg, few events to justify conducting an analysis). Listing of events will be provided in such situations. Additional analyses of the data may be conducted as deemed appropriate without further changes made to the protocol or SAP, even after the primary or final database locks (DBL).

Unless otherwise noted, all tests of treatment effects will be conducted at a 2-sided alpha level of 0.05, and the confidence interval will be calculated at 95%, 2-sided. In statistical summaries and analyses, all data will be analyzed by randomized treatment assignment. Participants will be analyzed according to the treatment they were randomly assigned to, regardless of the treatment actually received.

Baseline is defined as the last non-missing measurement recorded on or before the randomization visit, prior to first dose of treatment, unless otherwise specified. For lab, baseline needs to be prior to or within one hour after the first dose time. For patient reported outcomes, data collected at Visit 3, regardless of the timing relative to first dose, will serve as baseline.

There will be 2 estimands of interest in evaluating primary and secondary efficacy objectives. First estimand, the “treatment regimen” estimand, represents the efficacy irrespective of adherence to investigational product or introduction of rescue therapy for persistent severe hyperglycemia. Analysis relative to “treatment-regimen” estimand will be conducted using full analysis set. Second estimand, the “efficacy” estimand, represents efficacy prior to discontinuation of study drug or initiating rescue therapy for persistent severe hyperglycemia. Analysis relative to “efficacy” estimand will be conducted using efficacy analysis set. Safety will be assessed using safety analysis set. Selected safety analyses may be conducted after excluding data on rescue therapy or data after starting another antihyperglycemic medication.

End of study participation for a patient will be the earliest of date of death, date of withdrawal from further participation in the study, or date of safety follow-up visit (visit 801). For patients considered to be lost to follow-up, end of study participation will be the date of lost to follow-up reported by the investigator. Patient data included in database after the last date of study participation (date of death, date of early termination, or date of safety follow-up) will be excluded from statistical analysis. Listing of such data may be provided.

Summary statistics for continuous measures will include sample size, mean, standard deviation (SD), median, minimum, and maximum. Summary statistics for categorical measures (including categorized continuous measures) will include sample size, frequency, and percentages. Fisher’s exact test will be used to examine the treatment difference in categorical outcomes. Logistic

regression may be used to examine the treatment difference in binary efficacy outcomes. The negative binomial regression model will be used for the treatment comparison of discrete count measures if deemed appropriate.

The Kaplan-Meier method will be used for estimation of cumulative event-free rates over time, and cox proportional hazards regression analysis will be used to compare hazard rates among treatments.

Statistical treatment comparisons will only be performed between tirzepatide doses and placebo. Since the trials are not adequately powered to detect differences among tirzepatide doses, comparison among tirzepatide arms will not be performed unless otherwise specified.

4.2. Handling of Dropouts or Missing Data

For the primary and secondary efficacy endpoint analyses subject to type 1 error rate control, data for patients with missing values at the 40-week visit will be imputed based on the method described in Section 4.8.2. Unless specified otherwise, imputation of missing data will be limited to primary and key secondary efficacy endpoint analysis. Missing other secondary or exploratory efficacy parameter values and missing safety laboratory values will not be explicitly imputed unless otherwise specified.

4.3. Participant Dispositions

Frequency, counts and percentages of all participants screened, randomized, and receiving at least 1 dose of study intervention will be presented by treatment groups. Reasons for screen failure as reported by investigators will be summarized. A listing of randomized participants not receiving study intervention will be provided. Of the participants in the randomized population, frequency, counts and percentages of participants completing the study, prematurely discontinuing study, including the reason for premature discontinuation; and prematurely discontinuing study intervention, including the reason for premature discontinuation of study intervention will be presented by treatment group. A Kaplan-Meier analysis of time from randomization to premature discontinuation from study and premature discontinuation from study intervention by treatment group will be provided.

4.4. Patient Characteristics

All demographic and baseline clinical characteristics will be summarized by study treatment for all randomized patients. Baseline demographic and clinical characteristics of special interest include and not limit to: age, gender, weight, HbA1c, fasting serum glucose, duration of T2DM, eGFR.

Listing of patient demographics will be provided for all randomized patients.

4.5. Medical History and Preexisting Conditions

Medical history and pre-existing conditions will be summarized using the mITT population. Specific medical history regarding gallbladder diseases, pancreas, ketosis and diabetes complications may be summarized.

Listing of medical history and pre-existing conditions will be provided for mITT population.

4.6. Concomitant Therapy

The concomitant therapies will be mapped using the World Health Organization (WHO) DRUG dictionary in the clinical trial database and will be further classified using Anatomic-Therapeutic-Chemical (ATC) codes for reporting purposes. Concomitant medications will be summarized using the safety analysis set in mITT population. The prespecified concomitant medications of interest may be summarized by the planned treatment.

The concomitant medications of interest include the following groups of medication:

- baseline antihypertensive therapy, by type
- postbaseline antihypertensive therapy in Study Period II, by type
- baseline lipid lowering therapy, by type
- postbaseline lipid lowering therapy in Study Period II, by type
- prior use of antihyperglycemic therapy
- utilization of other antihyperglycemic therapy in Study Period II, and also in Study Period II and III
- rescue therapy due to severe persistent hyperglycemia
- initiation of following medications in Study Period II:
 - antidiarrheal medication
 - antiemetic medication

4.7. Important Protocol Deviation

Important protocol deviations is specified in Trial Issues Management Plan (TIMP). A listing and a summary of important protocol deviations (IPD) by treatment will be provided.

4.8. Primary Endpoint(s) Analysis

4.8.1. Definition of Endpoint(s)

The primary endpoint for this study is change in HbA1c (% and mmol/mol) from baseline at Week 40. This endpoint will be used to evaluate the primary objective of the study for both the treatment-regimen and efficacy estimands.

Both HbA1c values as well as change from baseline in HbA1c will be summarized by treatment and nominal visit (week). If scheduled HbA1c data at the primary endpoint visit is not available, unscheduled HbA1c data collected for the primary endpoint visit will be included in analysis.

4.8.2. Main Analytical Approach

The main analysis of primary endpoint will be based on treatment-regimen estimand. The analysis will be conducted utilizing HbA1c data in FAS at baseline and at the 40-week visit with the aid of an analysis of covariance (ANCOVA). The response variable will be the change in HbA1c from baseline at Week 40 and model terms will include treatment, any past prior use (yes or no) of any antihyperglycemic medication, and baseline HbA1c as covariates. Missing HbA1c values at Week 40 will be imputed using multiple imputation. Statistical inference over multiple imputations will be guided by the method proposed by (Rubin 1987).

Missing HbA1c data at the 40-week visit will be imputed based on “retrieved dropouts” defined as patients who had their HbA1c value measured at the 40-week visit in the same treatment arm who prematurely discontinued study drug, or used rescue therapy for persistent severe hyperglycemia. In cases where there are not enough retrieved dropouts to provide a reliable imputation model, an alternative multiple imputation method with reference to the placebo group (placebo multiple imputation) will be used. If value of the imputed HbA1c change from baseline is $<-6.0\%$ or $>6.0\%$, that value will be set to -6.0% or 6.0% , respectively, to avoid unrealistic imputed values.

With the aid of the ANCOVA analysis, p-values and 2-sided 95% confidence interval (CI) for mean change in HbA1c from baseline through 40-week visit for 5 mg, 10 mg, and 15 mg tirzepatide compared to placebo will be derived and summarized.

4.8.3. Supplementary Analyses

The analysis will be conducted utilizing HbA1c data in EAS from baseline through the 40-week visit with the aid of a mixed model for repeated measures (MMRM). Restricted maximum likelihood (REML) will be used to obtain model parameter estimates and Kenward-Roger option will be used to estimate denominator degrees of freedom. The response variable of the MMRM model will be the change in HbA1c from baseline at Week 40 and model terms will include treatment, visit, treatment by visit interaction, any past prior use (yes or no) of any antihyperglycemic medication, baseline HbA1c. Missing data will be addressed by the MMRM model under missing at random assumption. No explicit imputation methods for missing data will be employed.

An unstructured covariance structure will be used to model the within-patient errors. If this model fails to converge, the following covariance structures will be tested in order:

- Heterogeneous Toeplitz
- Heterogeneous First Order Autoregressive
- Heterogeneous Compound Symmetry
- Toeplitz
- First Order Autoregressive
- Compound Symmetry.

The first covariance structure that converges will be used. The resulting least squares mean (LSM) estimate of mean change from baseline in HbA1c will be summarized by visit and by study treatment.

With the aid of the MMRM analysis, p-values and 2-sided 95% confidence interval (CI) for mean change in HbA1c from baseline through 40-week visit for 5 mg, 10 mg, and 15 mg tirzepatide compared to placebo will be derived and summarized.

4.9. Secondary Endpoints Analysis

4.9.1. Key Secondary Endpoints (Controlled for Type 1 Error)

The secondary study objectives subject to type 1 error rate control are as follows:

- Proportion of participants with HbA1c target values of $<7.0\%$ (<53 mmol/mol)

- Change in fasting serum glucose from baseline
- Proportion of participants with HbA1c target values of $\leq 6.5\%$ (≤ 48 mmol/mol)
- Change in body weight from baseline
- Proportion of participants with HbA1c target values of $< 5.7\%$ (< 39 mmol/mol)

Key secondary endpoints will be evaluated based on the efficacy and treatment-regiment estimands (Section 3), similar to the primary endpoint.

4.9.1.1. Proportion of Participants with HbA1c Target Values of $< 7.0\%$, $\leq 6.5\%$ and $< 5.7\%$ at Week 40

Analysis relative to treatment-regimen estimand will be conducted by utilizing HbA1c data in FAS at baseline and at the 40-week visit with the aid of a logistic regression with multiple imputation of missing HbA1c data at the 40-week visit. The imputation method will be the same as the analysis of primary endpoint (see Section 4.8.2 for details). Model terms will include treatment, any past prior use (yes or no) of any antihyperglycemic medication, and baseline HbA1c as covariates. Statistical inference over multiple imputations will be guided by (Rubin 1987).

The analysis relative to the efficacy estimand for the endpoints at 40 weeks will be performed using EAS with missing values imputed from an MMRM model and then dichotomized. The MMRM model includes treatment, visit, treatment-by-visit interaction, and any past prior use (yes or no) of any antihyperglycemic medication, baseline HbA1c and baseline HbA1c-by-visit interaction. After dichotomizing continuous HbA1c, the data is analyzed using a logistic regression model with treatment, any past prior use (yes or no) of any antihyperglycemic medication, and baseline HbA1c as covariates.

4.9.1.2. Change in Fasting Serum Glucose and Body Weight From Baseline at the 40-Week Visit

The analysis for change in body weight and fasting serum glucose from baseline will be conducted in a manner similar to the primary analysis in Section 4.6. Baseline HbA1c category ($\leq 8.5\%$, $> 8.5\%$ [≤ 69 , > 69 mmol/mol]) will be used as a fixed factor in place of baseline HbA1c as a covariate and baseline of the corresponding variable will be used as an additional covariate in the statistical model. Least squares mean estimate of mean change in body weight and fasting serum glucose from baseline will be summarized by nominal visit and by study treatment. For the multiple imputation of missing values, if value of the imputed weight change from baseline is < -50 kg or > 50 kg, that value will be set to -50 kg or 50 kg, respectively, to avoid unrealistic imputed values; if value of the imputed fasting serum glucose change from baseline is < -20 mmol/L or > 20 mmol/L, that value will be set to -20 mmol/L or 20 mmol/L, respectively, to avoid unrealistic imputed values.

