4.11.4. Additional Safety Assessments

4.11.4.1. Hypoglycemic Events

Definitions of different categories of hypoglycemic events are included in [Table GPIU.4.3](#).

Table GPIU.4.3. Definitions of Hypoglycemic Event Categories

Glycemic Criteria/Description	
Level 1 (Glucose Alert Value)	Blood Glucose <70 mg/dL (3.9 mmol/L) and \geq 54 mg/dL (3.0 mmol/L)
Level 2 (Clinically Significant Hypoglycemia)	Glucose <54 mg/dL (3.0 mmol/L)
Level 3 (Severe Hypoglycemia)	A severe event characterized by altered mental and/or physical status requiring assistance for recovery (no specific glucose threshold).

Nocturnal hypoglycemia: a hypoglycemia event (including severe hypoglycemia) that occurs between bedtime and waking.

Severe hypoglycemia: Defined as an episode with severe cognitive impairment requiring the assistance of another person to actively administer carbohydrate, glucagon, or other resuscitative actions. Severe hypoglycemia will be reported as an SAE. Severe hypoglycemia will be considered as adverse event of special interest (AESI).

To avoid duplicate reporting, all consecutive blood glucose (BG) values <70 mg/dL (3.9 mmol/L) occurring within a 1-hour period may be considered to be a single hypoglycemic event.

Summaries and analyses will exclude hypoglycemic events occurring after initiation of a new antihyperglycemic therapy. For severe hypoglycemia and level 2 hypoglycemia, incidence as well as rate per patient year of exposure will be provided by treatment at specified time intervals. A listing of hypoglycemic events will also be provided. Safety analyses might be conducted after including data after the introduction of another antihyperglycemic therapy.

The incidence of hypoglycemic event will be analyzed using logistic regression with treatment and stratification factors as fixed effects. The rate of hypoglycemic episodes per patient year may be analyzed using a generalized linear mixed-effects model assuming the number of hypoglycemic episodes follows a negative binomial distribution with the mean modeled using stratification factors and treatment as fixed effects. When the number of hypoglycemic events is less 10, a listing of hypoglycemic events will be provided instead.

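### If no placebo participant is observed below HbA1c 5.7%, the logistic test in SAP 4.9.1.1 comes out non-significant for all three doses, and the section names no substitute

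*SAP*

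**What the plan says.** HbA1c <5.7% at Week 40 is a key secondary endpoint under type 1 error control, with one hypothesis per dose against placebo (H5,6, H10,6 and H15,6; SAP 2).

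- **Treatment-regimen estimand (SAP 4.9.1.1):** "logistic regression with multiple imputation of missing HbA1c data at the 40-week visit", with treatment, prior antihyperglycemic use and baseline HbA1c in the model. On pooling: "Statistical inference over multiple imputations will be guided by (Rubin 1987". Protocol 9.3.4 names the same model.
- **Efficacy estimand (SAP 4.9.1.1):** "missing values imputed from an MMRM model and then dichotomized". Then: "After dichotomizing continuous HbA1c, the data is analyzed using a logistic regression model with treatment". The section states neither the test statistic nor whether the imputation is single or multiple.
- **General text (SAP 4.1):** Fisher's "exact test will be used to examine the treatment difference in categorical outcomes". Logistic regression is listed there as an option for binary efficacy outcomes, and an analysis may be dropped when events are few.

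The SAP plans for breakdowns elsewhere. For the MMRM (4.8.3): "If this model fails to converge, the following covariance structures will be tested in order". For imputation (4.8.2): "In cases where there are not enough retrieved dropouts to provide a reliable imputation model, an alternative multiple imputation method". For hypoglycemia (4.11.4.1): "When the number of hypoglycemic events is less 10, a listing of hypoglycemic events will be provided instead". Section 4.9.1.1 has no corresponding step for an arm without responders.

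**The concern.** Participants enter with HbA1c between 7.0% and 9.5% on diet and exercise alone, and the placebo arm has about 50 of them. An observed placebo count of zero below 5.7% is therefore a realistic outcome. In that case the maximum-likelihood odds ratio against placebo is infinite. Rubin's rules need an estimate and a standard error from each imputed dataset, and the standard error is then a by-product of where the software stops iterating.

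Three confirmatory hypotheses would go unrejected for a numerical reason, and the larger the true contrast with placebo, the odder that result would look. The alternative is to choose another test once the data are known, which is what pre-specification is meant to avoid.

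**Working it through.** **Inputs.** 50 per arm (Protocol Synopsis and 9.5). The documents give no placebo rate for <5.7%. The only active rate is up to 62% on 15 mg in an earlier study (Protocol 2.2). The responder counts, missing counts, imputation probabilities and number of imputations below are assumptions. The plan states no power for this endpoint, so there is no figure to reproduce. The nearest, 0.01667 per dose (SAP 2.1), equals 0.05/3 but is stated only for the primary hypotheses.

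**1. Chance of an empty placebo cell**, (1 − p)^50:

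| Assumed true rate | 0.5% | 1% | 2% | 3% | 5% |
|---|---|---|---|---|---|
| P(0 of 50) | 78% | 61% | 36% | 22% | 8% |

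**2. One complete dataset, 20/50 against 0/50**, treatment only, Newton–Raphson:

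| Iterations | log OR | SE | Wald p |
|---|---|---|---|
| 8 | 8.80 | 14.1 | 0.53 |
| 15 | 15.8 | 467 | 0.97 |
| 25 | 25.8 | 69,247 | 0.9997 |

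At 8 iterations the active log odds are ln(20/30) = −0.41, so the fitted placebo log odds are −9.20 and the fitted rate is about 1.0e-4. The variance is 1/(50 × 0.4 × 0.6) + 1/(50 × 1.0e-4) ≈ 199, so SE ≈ 14.1. Each further iteration moves the placebo log odds down by about 1.

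With the SAP covariates (simulated values) and 10, 15 and 20 responders on the three doses, the p-values were 0.58, 0.55 and 0.53 at a loose tolerance and 0.999 for all three at a tight one.

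**3. Pooled over M = 100 imputations**, total variance T = W + (1 + 1/M)B, where W is the within- and B the between-imputation variance. Placebo has 0 of 47 observed and 3 missing, each imputed as a responder with probability 2, 5 or 10%. The numbers of empty datasets are 94, 85 and 73. The pooled p is 0.54, 0.54 and 0.55 at 8 iterations, 0.97, 0.97 and 0.98 at 15, and 0.9997 at 25.

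**4. When this does not happen.** No imputed dataset may be empty. With m missing placebo values imputed as responders with probability q, one dataset has a responder with probability 1 − (1 − q)^m. For m = 10 and q = 0.2 this is 0.893, so all datasets have one with probability 0.893^5 = 0.57 at M = 5, but about 1e-5 at M = 100. The SAP does not state M.

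A few empty datasets are usually enough. With 13 of 100 empty, p is 0.45 at 8 iterations and 0.98 at 15. The borderline case is one empty dataset in 100 at 8 iterations:

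- W = 0.01 × 14.09² + 0.99 × 1.05² ≈ 3.08
- B ≈ 0.28
- estimate 3.54, SE 1.83, p ≈ 0.054

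**5. Other tests on the same counts against 0/50:**

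| Active | ML Wald (8 iterations) | Fisher | Likelihood ratio | Risk difference, null variance | Firth, Wald |
|---|---|---|---|---|---|
| 20/50 | 0.53 | 1.8e-7 | 1.0e-8 | 5.7e-7 | 0.0040 |
| 10/50 | 0.58 | 0.0012 | 0.00011 | 0.00086 | 0.027 |

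For the risk difference with 20/50: z = 0.40/√(0.2 × 0.8 × 2/50) = 0.40/0.08 = 5.0. Pooled over the three scenarios of step 3 it gives 6.7e-7, 8.6e-7 and 1.2e-6.

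**6. One observed placebo responder.** 20/50 against 1/50 gives log OR 3.49, SE 1.05 and Wald p = 0.0009. Imputation never removes an observed responder, so a single participant decides whether the test works.

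**The case against.** **The event may be rare.** The FAS keeps data after rescue and after a switch to another glucose-lowering drug, and all participants receive lifestyle guidance. Each could produce a placebo responder. This stands: a reader might infer that an empty cell is expected, but the documents support only a range over assumed rates.

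**The SAP already names Fisher's exact test.** SAP 4.1 does, so it would be wrong to say that the plan contains no usable alternative. But 4.9.1.1 is the specific rule for this endpoint. Section 4.1 gives no trigger, no precedence and no way to pool Fisher's test over imputations. Its few-events clause permits dropping an analysis, which does not replace a confirmatory test.

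**A p-value near 1 is a limit.** This stands. At a loose convergence setting it is about 0.5. The Wald form is also inferred from the reference to Rubin's rules, although those rules leave little else.

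**Stronger readings that the documents do not support:**

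- *Type 1 error is inflated.* The failure is towards non-rejection.
- *The primary or other key secondary endpoints are compromised.* Nothing shows this, and any effect through the testing graph cannot be judged because the figure is not shown.
- *Both estimands fail alike.* For the efficacy estimand no test statistic is named. A likelihood-ratio p-value would survive there, though the odds ratio would still not be finite.

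**Conclusion.** The point holds for the treatment-regimen estimand and is worth fixing. With no observed placebo responder below 5.7%, the test as written is non-significant for H5,6, H10,6 and H15,6 together. For 20/50 against 0/50, p is about 0.5 to above 0.99, against 1.8e-7 by Fisher.

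This rests on three things: a Wald-type pooled test, zero observed placebo responders, and at least one empty imputed dataset. The last is near certain unless M is small and many placebo values are missing and often imputed below 5.7%. If only one or two of many datasets are empty and convergence is loose, the result is borderline instead of hopeless.

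How likely the situation is depends on a placebo rate that the documents do not give. The consequence is lost power on one controlled endpoint.

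**What to change.** Before unblinding, add a paragraph to SAP 4.9.1.1 for HbA1c <5.7% that:

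1. **Names one test that tolerates an empty cell.** An example is the risk difference stratified by the two randomisation factors, with null (score-type) variance for the test and unrestricted variance for the interval, pooled by Rubin's rules.
2. **Sets when it applies.** Either always, or whenever one arm of a comparison has no observed Week 40 responder in the analysis set of that estimand: FAS for treatment-regimen, EAS for efficacy. The sets must be named because a placebo responder seen only after rescue counts in the FAS but not in the EAS.
3. **States precedence** over the Fisher and few-events text of SAP 4.1.
4. **States whether the efficacy-estimand imputation is single or multiple**, and which test statistic is used.

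Apply the trigger by program at the final analysis. Do not check it on masked arm codes, because an arm with no responders would reveal placebo.

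**Does a data-dependent switch cost type 1 error?** Not in a simulation on assumed inputs (50 per arm, 6% missing, 20 imputations, common response rates of 1 to 10%, 2,000 replicates each). At a nominal 5%, rejection with the rule was at most 1.8% using the score-type test.

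**Cost.** One paragraph and a little programming, no new data. If the rule is triggered, <5.7% is reported as a risk difference with baseline HbA1c as a stratum, while <7.0% and ≤6.5% stay as odds ratios. Firth-penalised logistic regression would keep the scale and covariates but is conservative as a Wald test (10/50 against 0/50: 0.027, against 0.0012 by Fisher).
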